#### **4.10.1 Discontinuation of Study Therapy after CR**

Discontinuation of treatment may be considered for subjects who have attained a confirmed CR that have been treated for at least 24 weeks with pembrolizumab and had at least two treatments with pembrolizumab beyond the date when the initial CR was declared. Subjects who then experience radiographic disease progression may be eligible for up to one year of additional treatment with pembrolizumab via the Second Course Phase at the discretion of the investigator if no cancer treatment was administered since the last dose of pembrolizumab, the subject meets the safety parameters listed in the Inclusion/Exclusion criteria, and the trial is open. Subjects will resume therapy at the same dose and schedule at the time of initial discontinuation. Additional details are provided in Section 7.1.5.5.

#### **4.11 Clinical Criteria for Early Trial Termination**

Early trial termination will be the result of the criteria specified below:

1. Quality or quantity of data recording is inaccurate or incomplete
2. Poor adherence to protocol and regulatory requirements
3. Incidence or severity of adverse drug reaction in this or other studies indicates a potential health hazard to subjects
4. Plans to modify or discontinue the development of the study drug

In the event of Merck decision to no longer supply study drug, ample notification will be provided so that appropriate adjustments to subject treatment can be made.

## 5.0 TRIAL FLOW CHART

## 5.1 Study Flow Chart

Trial Period:	Screening Phase		Treatment Cycles							End of Study Treatment	Post-Study Treatment	
Treatment Cycle/Title:	Pre-screening (Visit 1)	Main Study Screening (Visit 2, Pre-RT)	Last Week of RT	1	2	3	To be repeated beyond 7 cycles				Safety Follow-up	Follow Up Visits Every 6 weeks (42 +/- 7 days) until to 48 weeks, then every 12 weeks (+/- 7 days) to 5 years
							4	5	6	7		
Scheduling Window (Days):		-45 to -1	± 7	± 3	± 3	± 3	± 3	± 3	± 3	± 3	At time of Discon	Approximately 30 days post discon
ECOG Performance Status		X	X	X	X	X	X	X	X	X	X	X
Laboratory Procedures/Assessments: analysis performed by LOCAL laboratory												
Pregnancy Test – Urine or Serum β-HCG		X										
Use of Birth Control		X										
PT/INR and aPTT		X										
CBC with Differential		X		X	X	X	X	X	X	X		
Comprehensive Serum Chemistry Panel		X		X	X	X	X	X	X	X		
Urinalysis		X										
T3, FT4 and TSH		X		X	X	X	X	X	X	X		
Pulmonary Function Tests		X								X (q6 cycles)	X	X
Quantitative Perfusion Scan (Cohort 1)		X 										
Renal Perfusion Scan (Cohort 1)		X 										
Efficacy Measurements												
Tumor Imaging			X				X			X – repeat every 3 cycles		X
Tumor Biopsies/Archival Tissue Collection/Correlative Studies Blood (Optional)												
Archival or Newly Obtained Tissue Collection		X										
Correlative Studies Blood Collection (as described in section 4.2.3.2)		X (ctDNA, CAF, immuno)	X (CAF, immuno)		X (CAF, immuno)					X (ctDNA, CAF, immuno)		

Trial Period:	Screening Phase		Treatment Cycles							End of Study Treatment	Post-Study Treatment	
Treatment Cycle/Title:	Pre-screening (Visit 1)	Main Study Screening (Visit 2, Pre-RT)	Last Week of RT	1	2	3	To be repeated beyond 7 cycles				Discon	Safety Follow-up
							4	5	6	7		
Scheduling Window (Days):		-45 to -1	± 7	± 3	± 3	± 3	± 3	± 3	± 3	± 3	At time of Discon	Approximately 30 days post discon
		CAF, immuno)	immuno)			immuno)						

**NOTE: All screening studies should be done within 45 days of radiation therapy. The exception to this guideline is laboratory tests, which should be done within 15 days of radiation therapy.**

Patients only need a quantitative perfusion scan and a renal scan if they enroll on cohort 1.

## 6.0 TRIAL PROCEDURES

### 6.1 Trial Procedures

The Trial Flow Chart - Section 6.0 summarizes the trial procedures to be performed at each visit. Individual trial procedures are described in detail below. It may be necessary to perform these procedures at unscheduled time points if deemed clinically necessary by the investigator.

Furthermore, additional evaluations/testing may be deemed necessary by the Sponsor and/or Merck for reasons related to subject safety. In some cases, such evaluation/testing may be potentially sensitive in nature (e.g., HIV, Hepatitis C, etc.), and thus local regulations may require that additional informed consent be obtained from the subject. In these cases, such evaluations/testing will be performed in accordance with those regulations.

#### 6.1.1 Administrative Procedures

##### 6.1.1.1 Informed Consent

The Investigator must obtain documented consent from each potential subject prior to participating in a clinical trial.

###### 7.1.1.1 General Informed Consent

Consent must be documented by the subject's dated signature or by the subject's legally acceptable representative's dated signature on a consent form along with the dated signature of the person conducting the consent discussion.

A copy of the signed and dated consent form should be given to the subject before participation in the trial.

The initial informed consent form, any subsequent revised written informed consent form and any written information provided to the subject must receive the IRB/ERC's approval/favorable opinion in advance of use. The subject or his/her legally acceptable representative should be informed in a timely manner if new information becomes available that may be relevant to the subject's willingness to continue participation in the trial. The communication of this information will be provided and documented via a revised consent form or addendum to the original consent form that captures the subject's dated signature or by the subject's legally acceptable representative's dated signature.

Specifics about a trial and the trial population will be added to the consent form template at the protocol level.

The informed consent will adhere to IRB/ERC requirements, applicable laws and regulations and Sponsor requirements.

## **6.1.1.2 Inclusion/Exclusion Criteria**

All inclusion and exclusion criteria will be reviewed by the investigator or qualified designee to ensure that the subject qualifies for the trial.

## **6.1.1.3 Medical History**

A medical history will be obtained by the investigator or qualified designee. Medical history will include all active conditions, and any condition diagnosed within the prior 10 years that are considered to be clinically significant by the Investigator. Details regarding the disease for which the subject has enrolled in this study will be recorded separately and not listed as medical history.

## **6.1.1.4 Prior and Concomitant Medications Review**

### **6.1.1.4.1 Prior Medications**

The investigator or qualified designee will review prior medication use, including any protocol-specified washout requirement, and record prior medication taken by the subject within 28 days before starting the trial. Treatment for the disease for which the subject has enrolled in this study will be recorded separately and not listed as a prior medication.

### **6.1.1.4.2 Concomitant Medications**

The investigator or qualified designee will record medication, if any, taken by the subject during the trial. All medications related to reportable SAEs and ECIs should be recorded as defined in Section 7.2.

## **6.1.1.5 Disease Details and Treatments**

### **6.1.1.5.1 Disease Details**

The investigator or qualified designee will obtain prior and current details regarding disease status.

### **6.1.1.5.2 Prior Treatment Details**

The investigator or qualified designee will review all prior cancer treatments including systemic treatments, radiation and surgeries.

### **6.1.1.5.3 Subsequent Anti-Cancer Therapy Status**

The investigator or qualified designee will review all new anti-neoplastic therapy initiated after the last dose of trial treatment. If a subject initiates a new anti-cancer therapy within 30 days after the last dose of trial treatment, the 30 day Safety Follow-up visit must occur before the first dose of the new therapy. Once new anti-cancer therapy has been initiated the subject will move into survival follow-up.

**6.1.2 Clinical Procedures/Assessments****6.1.2.1 Adverse Event (AE) Monitoring**

The investigator or qualified designee will assess each subject to evaluate for potential new or worsening AEs as specified in the Trial Flow Chart and more frequently if clinically indicated. Adverse experiences will be graded and recorded throughout the study and during the follow-up period according to NCI CTCAE Version 4.0 (see Section 11.2). Toxicities will be characterized in terms regarding seriousness, causality, toxicity grading, and action taken with regard to trial treatment.

For subjects receiving treatment with pembrolizumab all AEs of unknown etiology associated with pembrolizumab exposure should be evaluated to determine if it is possibly an event of clinical interest (ECI) of a potentially immunologic etiology (termed immune-related adverse events, or irAEs); see the separate ECI guidance document in Appendix 4 regarding the identification, evaluation and management of potential irAEs.

Please refer to section 7.2 for detailed information regarding the assessment and recording of AEs. Adverse events will be recorded in the Prometheus database. We will capture all adverse events (related to radiation therapy, pembrolizumab, or a combination of the two). AE's will be collected weekly during radiation therapy and grade 3 or higher toxicities will be documented. The PI or designee will be responsible for determining attribution for all events, which will also be documented in the Prometheus database.

**6.1.2.2 Full Physical Exam**

The investigator or qualified designee will perform a complete physical exam during the screening period. Clinically significant abnormal findings should be recorded as medical history. A full physical exam should be performed during screening,

**6.1.2.3 Directed Physical Exam**

For cycles that do not require a full physical exam per the Trial Flow Chart, the investigator or qualified designee will perform a directed physical exam as clinically indicated prior to trial treatment administration.

**6.1.2.4 Vital Signs**

The investigator or qualified designee will take vital signs at screening, prior to the administration of each dose of trial treatment and at treatment discontinuation as specified in the Trial Flow Chart (Section 6.0). Vital signs should include temperature, pulse, respiratory rate, weight and blood pressure. Height will be measured at screening only.

**6.1.2.5 Eastern Cooperative Oncology Group (ECOG) Performance Scale**

The investigator or qualified designee will assess ECOG status (see Section 11.1) at screening, prior to the administration of each dose of trial treatment and discontinuation of trial treatment as specified in the Trial Flow Chart.

**6.1.2.6 Tumor Imaging and Assessment of Disease**

Patients will have their history collected at screening, and a physical exam will be performed at screening, post-RT (+/- 7 days), on day 1 of each pembrolizumab cycle, at the end of treatment visit, and post-treatment. Patients will be imaged with either: 1) CT scan of the chest with contrast, or 2) PET/CT scan. This imaging will be done with the following frequency: prior to radiation therapy, after cycle 3 of pembrolizumab, and every 3 cycles thereafter. Pulmonary function tests will be done at the following timepoints: 1) At enrollment, 2) after every 6 cycles of pembrolizumab, and 3) at the discontinuation of treatment.

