## 4.4 Trial Treatments

The treatment to be used in this trial is outlined below in Table 2

Table 2 Trial Treatment

Drug	Dose/Potency	Dose Frequency	Route of Administration	Regimen/Treatment Period	Use
Pembrolizumab	200 mg X mg/kg	Q3W	IV infusion	Day 1 of each 3 week cycle	Experimental

Note: Patients must initiate treatment with Pembrolizumab within 1 month of the last day of radiation therapy.

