# Proprietary Information of MD Anderson

2015-0856

Version 23

Page 17

Toxicity	Hold Treatment For Grade	Timing for Restarting Treatment	Discontinue Subject/Off-Study Criteria (“Unacceptable” Toxicities)
Diarrhea/Colitis	2-3	Toxicity resolves to Grade 0-1.	Toxicity does not resolve within 12 weeks of last dose or inability to reduce corticosteroid to 10 mg or less of prednisone or equivalent per day within 12 weeks.
	4	Permanently discontinue	Permanently discontinue/Off-Study
AST, ALT, or Increased Bilirubin	2	Toxicity resolves to Grade 0-1	Toxicity does not resolve within 12 weeks of last dose.
	3-4	Permanently discontinue (see exceptions below) 	Permanently discontinue/Off-Study
Type 1 diabetes mellitus (if new onset) or Hyperglycemia	T1DM or 3-4	Hold pembrolizumab for new onset Type 1 diabetes mellitus or Grade 3-4 hyperglycemia associated with evidence of beta cell failure.	Resume pembrolizumab when patients are clinically and metabolically stable.
Hypophysitis	2-3	Toxicity resolves to Grade 0-1	Toxicity does not resolve within 12 weeks of last dose or inability to reduce corticosteroid to 10 mg or less of prednisone or equivalent per day within 12 weeks.
	4	Permanently discontinue	Permanently discontinue/Off-Study
Hyperthyroidism	3	Toxicity resolves to Grade 0-1	Toxicity does not resolve within 12 weeks of last dose or inability to reduce corticosteroid to 10 mg or less of prednisone or equivalent per day within 12 weeks.
	4	Permanently discontinue	Permanently discontinue/Off-Study
Hypothyroidism	2-4	Therapy with pembrolizumab can be continued while treatment for the thyroid disorder is instituted	Therapy with pembrolizumab can be continued while treatment for the thyroid disorder is instituted.
Infusion Reaction	3-4	Permanently discontinue	Permanently discontinue/Off-Study
Pneumonitis	2	Toxicity resolves to Grade 0-1	Toxicity does not resolve within 12 weeks of last dose or inability to reduce corticosteroid to 10 mg or less of prednisone or equivalent per day within 12 weeks. Recurrent grade 2 pneumonitis requires discontinuation of pembrolizumab.
	3-4	Permanently discontinue	Permanently discontinue/Off-Study
Renal Failure or Nephritis	2	Toxicity resolves to Grade 0-1	Toxicity does not resolve within 12 weeks of last dose or inability to reduce corticosteroid to 10 mg or less of prednisone or equivalent per day within 12 weeks.
	3-4	Permanently discontinue	Permanently discontinue/Off-Study

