#### **4.4.2 Timing of Dose Administration**

Trial treatment should be administered on Day 1 of each cycle after all procedures/assessments have been completed as detailed on the Trial Flow Chart (Section 6.0). Trial treatment may be administered up to 3 days before or after the scheduled Day 1 of each cycle due to administrative reasons.

All trial treatments will be administered on an outpatient basis at MDACC.

Pembrolizumab 200 mg will be administered as a 30 minute IV infusion every 3 weeks for up to 2 years

Sites should make every effort to target infusion timing to be as close to 30 minutes as possible. However, given the variability of infusion pumps from site to site, a window of -5 minutes and +10 minutes is permitted (i.e., infusion time is 30 minutes: -5 min/+10 min).

The Pharmacy Manual contains specific instructions for the preparation of the pembrolizumab infusion fluid and administration of infusion solution.

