#### **6.1.5.4 Follow-up Visits**

Subjects who discontinue trial treatment for a reason other than disease progression will move into the Follow-Up Phase and should be assessed every 6 weeks ( $42 \pm 7$  days) by radiologic imaging to monitor disease status. After 48 weeks the imaging time point will occur every 12 weeks ( $\pm 7$  days), up to 5 years. Every effort should be made to collect information regarding disease status until the start of new anti-neoplastic therapy, disease progression, death, end of the study or if the subject begins retreatment with pembrolizumab as detailed in Section 7.1.5.5. Information regarding post-study anti-neoplastic treatment will be collected if new treatment is initiated.

Subjects who are eligible to receive retreatment with pembrolizumab according to the criteria in Section 7.1.5.5 will move from the follow-up phase to the Second Course Phase when they experience disease progression. Details are provided in Section 6.2 – Trial Flow Chart for Retreatment.

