If the true toxicity rate is 0.50, there is a 65.0% probability of stopping the trial early.

Descriptive statistics will be used to summarize the study data. For each study cohort, we will tabulate toxicities by dose, severity, and relationship to the treatment plan. The method of Kaplan and Meier will be used to estimate median PFS and OS.

A Toxicity/Efficacy Summary will be submitted to the IND Medical Monitor after the first 6 evaluable subjects per cohort, complete 4 months from the initiation of Radiation Therapy and prior to the enrollment of the next cohort, and following the treatment of the next 6 evaluable subjects to each cohort.

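### On-treatment scans are counted in pembrolizumab cycles, so a dose hold can postpone the scan that dates progression; the effect on PFS is modest, but scan dates should be fixed to the calendar

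*Combined protocol and SAP*

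**What the plan says.** **On treatment.** Section 6.1.2.6 states: "This imaging will be done with the following frequency: prior to radiation therapy, after cycle 3 of pembrolizumab, and every 3 cycles thereafter". The flow chart in Section 5.1 uses the same unit, "X – repeat every 3 cycles". Table 2 (Section 4.4) gives pembrolizumab on "Day 1 of each 3 week cycle", and Section 4.4.2 adds: "Trial treatment should be administered on Day 1 of each cycle after all procedures/assessments have been completed". A cycle therefore opens with a dose.

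**Holds.** For several toxicities Table 3 (Section 4.4.1.2) withholds the drug until recovery. The patient leaves treatment if "Toxicity does not resolve within 12 weeks of last dose". The notes below the table also allow interruptions for unrelated medical or logistical reasons, with return within 3 weeks unless otherwise discussed.

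**Off treatment.** Under Section 6.1.5.4, patients who stop for a reason other than progression "will move into the Follow-Up Phase and should be assessed every 6 weeks". It continues: "After 48 weeks the imaging time point will occur every 12 weeks". These are calendar intervals.

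**Analysis.** PFS is a secondary objective, with a hypothesis of improvement over historical controls (Section 3.2). Section 7.2 says: "The method of Kaplan and Meier will be used to estimate median PFS and OS". It gives no interval-censored analysis and no sensitivity analysis for scan timing.

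Nowhere does the plan say that on-treatment scans keep to the calendar while a dose is held.

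**The concern.** Radiographic progression can be dated only when a scan is done. If the next scan waits for doses to be given, a patient whose drug is held for toxicity is scanned later than one treated without interruption, and the same disease course gets a later progression date. Table 3 includes holds for Grade 2 pneumonitis, a central risk after chest irradiation, so such holds are foreseeable.

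The PFS curve would then reflect drug tolerance as well as disease control. Late detection lengthens apparent PFS, the direction that favours the Section 3.2 hypothesis.

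**Working it through.** The plan states no PFS figure to reproduce, so the check is of the scan interval and the detection lag.

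**1. Scan interval.** Inputs: 3-week cycles, a scan every 3 cycles, and a limit of 12 weeks from the last dose. If a held dose defers its cycle, interval = 3 × 3 + d weeks, where d is the extra delay.
- No hold: 9 weeks.
- Interruption taken as 3 extra weeks: 9 + 3 = 12 weeks.
- Dose given 12 weeks after the previous one instead of 3: d = 12 − 3 = 9, so 9 + 9 = 18 weeks.

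For progression spread evenly over the affected interval, mean lag is half its length: 4.5, 6.0 and 9.0 weeks. That applies only to patients who progress in that interval.

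**2. Mean lag over all progressions in a held patient.** Assume exponential PFS from the first dose and one hold, equally likely in scan interval 1, 2 or 3. The median is 26 or 44 weeks (both assumed), or 66.9 weeks (the 15.4-month median disease-free survival in Section 4.1). Let λ = ln 2 / median and S(t) = exp(−λt).

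Worked example, median 26 weeks: 1/λ = 37.51, S(9) = 0.787, S(18) = 0.619.
- No hold: mean recorded time = 9 / (1 − 0.787) = 42.19 (unrounded S), so lag = 42.19 − 37.51 = 4.68.
- 9-week hold in interval 1: 18 + 0.619 × 42.19 = 44.11, lag 6.60.
- In interval 2: 9 + 0.787 × 44.11 = 43.70, lag 6.19.
- In interval 3: 9 + 0.787 × 43.70 = 43.38, lag 5.87.
- Average over the three: 6.22, an excess of 6.22 − 4.68 = 1.54 weeks.

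All three medians, treated the same way (weeks):

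| Assumed median | Lag, no hold | Lag, 3 extra weeks | Excess | Lag, 9 extra weeks | Excess |
|---|---|---|---|---|---|
| 26 | 4.68 | 5.04 | 0.36 | 6.22 | 1.54 |
| 44 | 4.61 | 4.84 | 0.24 | 5.65 | 1.04 |
| 66.9 | 4.57 | 4.74 | 0.17 | 5.30 | 0.73 |

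A simulation of 400,000 patients per scenario agrees. (Excesses are from unrounded values.)

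**3. Cohort level.** The documents give no frequency of holds. If 10% to 40% of patients had one maximal hold (assumed), the cohort mean would shift by 0.10 × 1.04 = 0.1 to 0.40 × 1.54 = 0.6 weeks.

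**4. Recorded median.** In the simulation, the recorded median without holds and with 9 extra weeks in every patient is 27 and 36 weeks (true median 26), 45 and 45 (true 44), and 72 and 72 (true 66.9). The first pair moves because the week-27 scan falls just beyond the true median; there, holding 30% of patients is enough for the jump. The shift is a property of the scan grid. For scale, the sample median of 12 uncensored exponential times with true median 26 weeks has a standard deviation of about 11 weeks.

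**5. With the calendar fix.** The interval stays at 9 weeks with or without a hold, and the excess is zero.

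**The case against.** The strongest reply is that PFS here is secondary, descriptive and single-arm, with 12 patients per cohort. A shift of a week or so in a held patient is small beside sampling error. That stands, and it limits the importance of the point. It does not remove the dependence on toxicity, which costs little to prevent.

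Second, the plan does not say whether a held dose defers a cycle or skips it. If skipped cycles counted, scans would stay 9 weeks apart. Deferral is the natural reading, because a cycle opens with a dose and Section 4.10 also counts treatment in administrations (35). The silence itself needs closing. Section 6.1 permits unscheduled procedures when clinically necessary, which may shorten some delays, but it is discretionary.

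Three stronger readings are tempting and are not supported:
- *A mean delay near 10 weeks.* Scans every 18 weeks throughout would give 9.7 weeks at a 26-week median, but that needs a maximal hold in every interval. Table 3 and its note require permanent discontinuation for recurrent Grade 2 pneumonitis and recurrent Grade 3 drug-related events, so repeated maximal holds are implausible.
- *Progression goes unrecorded until three further cycles are given.* A hold falls inside a three-cycle block, so only the rest of that block is outstanding.
- *Patients who stop for toxicity are scanned every 6 weeks and so recorded as progressing earlier.* Sections 4.10 and 6.1.5.4 point to continued disease assessment, 6-weekly at first. Section 6.1.4.1 describes follow-up until symptoms resolve and then for survival, by clinic visit or telephone. The documents do not settle whether these patients are scanned, so no direction of bias can be claimed.

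The 9-week figure counts from the first dose. The first gap from the pre-radiation scan is longer for everyone: in Cohort 1, about 5 weeks of radiation (25 fractions, assuming five a week), up to 1 month before pembrolizumab, then 9 weeks, or up to about 18 weeks with no toxicity.

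**Conclusion.** The point holds as a scheduling weakness of modest size. Because on-treatment scans follow cycles, one hold can stretch one scan interval from 9 weeks to at most 18 and postpone recorded progression by up to 9 weeks in an affected patient. Averaged over progressions in a held patient, the added lag is about 1.0 to 1.5 weeks for one maximal hold at an assumed median of 26 to 44 weeks (0.7 at 66.9), and about 0.2 to 0.4 weeks for a 3-week interruption.

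This rests on deferral of held cycles, a single hold in one of the first three intervals, exponential PFS, and no unscheduled scans. The primary toxicity endpoint and the stopping rule in Section 7.2 do not use scan dates and are unaffected. Separately, follow-up for progression after stopping for toxicity is described inconsistently and must be reconciled.

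**What to change.** 1. In Section 6.1.2.6 and the flow chart, replace the cycle count with fixed calendar times from the first pembrolizumab dose, at the existing nominal 9-week interval with a window such as ± 7 days. State that dose holds and interruptions do not move scan dates.
2. Reconcile Section 6.1.4.1 with Sections 4.10 and 6.1.5.4, so that patients who stop for toxicity have one stated calendar schedule for PFS ascertainment.

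The off-treatment interval need not be lengthened to match. Going from 6 to 9 weeks would cut scans over 48 weeks from 48/6 = 8 to about 5 (48/9 = 5.3), a real loss of surveillance that this fix does not require.

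The cost is wording in a few sections. Scan numbers on treatment stay about the same, since held patients are simply scanned on time. The small downside is that a scan may not coincide with a dosing visit.
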